### **3.3 Data Sources/Data Collection Process**

#### **3.3.1 Data Sources**

The data sources of this non-interventional observational study are Case Report Forms (CRFs) and patient questionnaires. Collection of data includes but not limited to subject demographics, clinical history, comorbidities, spontaneous adverse events, and concomitant medications. The following questionnaires will be utilized to collect data directly from participating subjects:

- HAQ DI
- SF-36
- EQ-5D-3L
- WPAI
- Patient Global Impression of Change (PGIC)
- Patient Treatment Satisfaction Questions
- HCRU

#### **3.3.2 Data Collection**

IMS will coordinate data collection with each site. At study initiation (Baseline, D0), patients will be asked to provide their written informed consent. After signing consent, the patients' questionnaires as recorded will be collected. At Week 12 and 24 time-points, the patients' questionnaires will be collected before them visiting their physicians. There will be a study coordinator or study nurse at each site to monitor the process. The study coordinator/nurse will collect the record of questionnaires directly. Physicians will not see the contents patients entered. The study coordinator/nurse will check to ensure all the forms are filled-in correctly.

In addition, physicians will also be asked to complete a clinical CRF in paper form based on the patient's medical records at baseline, 12 weeks, and 24 weeks. The CRF completed by physicians will be returned to the study coordinator/nurse at each site as well.

All data will be collected by the study coordinator/nurse at each site and returned directly to IMS. The data collection time is expected to be 10-13 months.

All patient and clinician data will be handled preserving confidentiality.

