9.2.4.6 Data Collection

AbbVie will coordinate data collection with each site. At study initiation (Baseline, D0), patients will be asked to provide their written informed consent.

When available, the PRO data as observed will be collected -. The CRF completed by physicians will be returned to the study coordinator/nurse at each site as well.

All data filled in by the patient and physician will be collected by the study coordinator/nurse at each site and returned directly to AbbVie.

All patient and clinician data will be handled preserving confidentiality.

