The WPAI is a patient-reported questionnaire to measure work and activity impairment during the past seven days. It determines employment status, hours missed from work due to the disease (i.e. RA), hours missed from work for other reasons, hours actually worked, the degree to which the disease affected work productivity while at work and the degree to which the disease affected activities outside of work. Additional questions around employment status will be incorporated into the survey. The completion time for the WPAI is approximately 2-5 minutes. The full version of WPAI is presented in **Error! Reference source not found.**

All of the above questionnaires will be used with the validated Chinese version.

Patient Global Impression of Change (PGIC)

The PGIC measures the patient's perceptions of changes in their disease. It consists of one question asking about the change in their condition; for this study, the base will be "since you initiated your adalimumab treatment". The completion time for the PGIC is less than 1 minute. The full version of PGIC is presented in **Error! Reference source not found.**

Patient Treatment Satisfaction Questions

The patient treatment satisfaction questions were developed de novo for this study and are not considered "validated" questions. Self-administered by the patient, the completion time for the patient treatment satisfaction questions is approximately 1-2 minutes. The full version of patient treatment satisfaction questions are presented in **Error! Reference source not found.**

Healthcare Resource Utilization (HCRU) Questionnaire

The HCRU questionnaire will collect data on the healthcare resources consumed in the prior 3 months, as recall beyond 3 months may be problematic in an older population (16). HCRU collection will include data such as the number of physician visits and to which physician (GP, specialist), Emergency Department visits, hospitalizations, and other drugs as well as devices and aids purchased to assist in their mobility due to RA. The HCRU questionnaire will be part of the patient questionnaire and will be distributed to patients together with the PRO questionnaires (Appendix D to Appendix I). The full HCRU questionnaire is presented in **Error! Reference source not found.J** and will be used with the validated Chinese version.

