11.0 Management and Reporting of Adverse Events/Adverse Reactions

11.1 Adverse Event Definition and Serious Adverse Event Categories

An adverse event (AE) is defined as any untoward medical occurrence in a patient, which does not necessarily have a causal relationship with their treatment. An adverse event can therefore be any unfavorable and unintended sign (including an abnormal laboratory finding), symptom, or disease temporally associated with the use of a medicinal product, whether or not the event is considered causally related to the use of the product.

Such an event can result from use of the drug as stipulated in the labeling, as well as from accidental or intentional overdose, drug abuse, or drug withdrawal. Any worsening of a pre-existing condition or illness is considered an adverse event.

If an adverse event meets any of the following criteria, it is considered a serious adverse event (SAE):

Death of Patient:	An event that results in the death of a patient.
Life-Threatening:	An event that, in the opinion of the investigator, would have resulted in immediate fatality if medical intervention had not been taken. This does not include an event that would have been fatal if it had occurred in a more severe form.
Hospitalization:	An event that results in an admission to the hospital for any length of time. This does not include an emergency room visit or admission to an outpatient facility.
Prolongation of Hospitalization:	An event that occurs while the study patient is hospitalized and prolongs the patient's hospital stay.
Congenital Anomaly:	An anomaly detected at or after birth, or any anomaly that results in fetal loss.
Persistent or Significant Disability/Incapacity:	An event that results in a condition that substantially interferes with the activities of daily living of a study patient. Disability is not intended to include

experiences of relatively minor medical significance such as headache, nausea, vomiting, diarrhea, influenza, and accidental trauma (e.g., sprained ankle).

Important Medical Event Requiring Medical or Surgical Intervention to Prevent Serious Outcome:

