11.5 Serious Adverse Event Reporting

In the event of a serious adverse event, the physician will:

- For events from patients using an AbbVie product - notify the AbbVie Emergency contact person (ASR) identified at the beginning of the protocol within 24 hours of the physician becoming aware of the event.

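### Admissions that patients report only on the HCRU form are kept from the physician, whose awareness starts the SAE clock, and no step reconciles the two data streams

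*SAP*

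**What the plan says.** Protocol 9.2.4.7 makes HCRU a patient-completed form: "The HCRU questionnaire will be part of the patient questionnaire and will be distributed to patients together with the PRO questionnaires". It looks back a quarter of a year: "The HCRU questionnaire will collect data on the healthcare resources consumed in the prior 3 months". Protocol Table 1 schedules it at baseline, week 12, week 24 and early termination. SAP 3.3.1 lists it among the patient questionnaires.

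SAP 3.3.2 has the week 12 and week 24 questionnaires collected before the patient sees the physician, and adds: "Physicians will not see the contents patients entered". Protocol 9.2.4.6 contains no such restriction. It says only that "All data filled in by the patient and physician will be collected by the study coordinator/nurse at each site and returned directly to AbbVie". The SAP sends the same forms to a contractor instead.

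On safety, one hospitalisation criterion for an SAE in Protocol 11.1 is "An event that results in an admission to the hospital for any length of time". The same section states: "Any worsening of a pre-existing condition or illness is considered an adverse event". Protocol 11.5 places the reporting duty on the physician, "within 24 hours of the physician becoming aware of the event".

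**The concern.** Keeping patients' answers about function and quality of life from the treating physician protects those outcomes from influence. Applied to HCRU, the same rule withholds a form on which patients are asked about admissions from the person who must report SAEs and rate their severity and causality (Protocol 11.2, 11.3).

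Two things are at stake. An SAE could reach the safety system weeks late, or be missed. The study could also report RA-related hospitalisations as resource use that its SAE data do not contain, with no planned step to reveal the mismatch.

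**Working it through.** No formula bears on this point, and the documents state no figure to reproduce. The check follows one admission through the text.

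1. **When an admission is an SAE.** Under Protocol 11.1 there must first be an adverse event, and that event must lead to admission. Worsening of existing disease counts as an adverse event. Protocol 11.4 collects SAEs from consent to 70 days after the last dose. An admission for an RA flare after consent therefore qualifies. An admission before consent, or one not caused by an adverse event, does not. An emergency room visit alone does not meet the hospitalisation criterion, but it may point to an event that needs assessment.

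2. **Where the patient discloses it.** It goes on the HCRU form at the next scheduled visit. Suppose a patient is admitted to another hospital for a flare in week 5 and writes it on the week 12 form.

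3. **Who sees the form.** The site coordinator or nurse does; under SAP 3.3.2 the physician does not. The coordinator's stated check is that forms are complete and properly filled in (Protocol 9.2.4.4 and 9.8.2, SAP 3.3.2). The physician fills in the CRF from the medical records, which may not show an admission elsewhere.

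4. **Who must act.** Protocol 11.5 starts 24 hours from the physician's awareness. Protocol 12.1 gives a second route: staff who handle patient data are trained to recognise adverse events and tell the Affiliate Safety Specialist, with a time limit that runs from discovery. The two sections use different starting points, and 12.1 describes no path back to the investigator.

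5. **Who compares the streams.** Nobody is told to. Sponsor review of questionnaires concerns accuracy and completeness, and a complete, internally consistent form need raise no query. SAP 5.5 tabulates RA-related hospitalisations in Excel Table 9. The table list in SAP section 6 has no adverse event or SAE table, although Protocol 9.7.8 plans SAE summaries.

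**Scale only, not an estimate of missed events:**
- Post-baseline forms: 52 patients × 2 visits = 104 if everyone completes. With the planned 10% dropout, 52 × 0.90 = 46.8, about 47 completers, and 47 × 2 = 94 forms. Early-termination forms add to this. Collection only when available (Protocol 9.1) reduces it.
- Delay: week 12 − week 5 = 7 weeks in the example. With visits 12 weeks apart, an admission can be about 12 weeks old when written down.
- Weight of one patient: 1/52 = 1.9 percentage points of the SAE proportion.
- Look-back: taking 3 months as about 13 weeks (an assumption), the week 12 form reaches about 13 − 12 = 1 week before baseline. Admission dates are therefore needed to separate events before and after consent.

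**The case against.** The strongest reply is that the physician's view of this form is not the only safeguard.

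- Protocol 11.6 requires SAEs to be actively solicited, and at weeks 12 and 24 the patient sees the physician after handing in the forms.
- Protocol 9.2.5 records adverse events noticed by site personnel or volunteered by the patient.
- Protocol 12.1 can be read to cover the coordinator as well as data staff.
- Protocol 9.8.2 and SAP 3.3.4 plan full source review for safety and logic checks, and Protocol 12.3 adds calls to sites at least every two weeks.
- Protocol 9.2.6 adds a safety call about 70 days after the last dose for patients who stop the drug.

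All of this stands, and it rules out several stronger readings. A reader might infer that only an aware physician must report. That is true of 11.5 alone, because 12.1 supplies another route. A reader might infer that such events would never be reported. The safeguards above do not allow that conclusion. A reader might treat every admission on the form as an SAE. Sections 11.1 and 11.4 limit this to admissions caused by an adverse event within the collection period, and the baseline form looks back before it. Finally, a pneumonia admission may not appear in Excel Table 9 at all, since the SAP tabulates RA-related admissions only. The questionnaire itself is a separate document, so whether it asks about all admissions or only RA-related ones cannot be checked here.

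What the reply does not supply is a specific link. No safeguard mentions HCRU, sends its content to the investigator, or requires a comparison. Withholding the form also works against the active solicitation that 11.6 demands.

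**Conclusion.** The gap is real but narrow. An admission that results from an adverse event after consent and is disclosed only on the HCRU form may enter the resource-use table while its SAE report comes late or not at all. This follows from SAP 3.3.2, Protocol 11.5 and the absence of any reconciliation step. The access restriction stands in the SAP and not in Protocol 9.2.4.6, so the two documents also need aligning.

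The size cannot be estimated, because the documents give no admission or SAE rate. The 1.9 points per patient shows only how much one event weighs in a study of about 52. The primary HAQ DI analysis and the power calculation are unaffected.

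The conclusion assumes that the restriction applies to HCRU as written and that no separate safety or data-management plan provides the missing link. The change is worth making because it is cheap and leaves the other patient-reported answers shielded.

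**What to change.** 1. In SAP 3.3.2, limit the restriction on physician access to HAQ DI, SF-36, EQ-5D, WPAI, PGIC and the satisfaction questions. Put matching text in Protocol 9.2.4.6.
2. Have the coordinator read each post-baseline HCRU form (week 12, week 24, early termination) on the day it is handed in. Any hospitalisation, emergency visit or surgery dated after consent goes to the investigator that day for AE/SAE assessment.
3. Reconcile the awareness and notification wording of Protocol 11.5, Protocol 12.1 and SAP 3.3.2, so that it is clear when the 24 hours begin if site staff learn of an event first, and how it reaches the investigator.
4. Before the analysis is finalised, run one listing of HCRU hospitalisations and surgeries against the SAE data, and resolve mismatches with the investigator.

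The cost is document wording, a few minutes of coordinator time per visit and one listing. The drawback is that physicians see resource-use answers, which are not the primary endpoint. SAP V0.4 (May 2019) is later than the planned end of data collection (30 June 2018). If visits are over, steps 1 and 2 come too late to help, but step 4 can still be done on the data already collected.

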### **3.3.3 Ethics and Quality**

Prior to any study-related data being collected, informed consent form will be reviewed, signed and dated by the patient and the person who administered the informed consent. A copy of the signed informed consent will be given to the patient and the original will be placed in the patient's medical record.

### **3.3.4 Quality Assurance**

Prior to the initiation of the study, physician and site personnel will be trained on the study. Training will include a detailed discussion of the protocol, performance of study procedures, and completion of the CRFs and paper questionnaires.

All sites will be monitored during the course of study participation. One hundred percent (100%) source document review for safety will be performed.

All clinical data will be documented via the CRF. Study coordinators at each site will check the paper CRFs completed by the physicians and questionnaires completed by patients (e.g., all questions were answered). Data entry will be conducted by IMS. After entry of the data, computer logic checks will be run to check for inconsistent data. Any necessary corrections will be made to the database and documented via addenda, queries, and source data clarification forms.

Steps to be taken to ensure the accuracy and reliability of data include the selection of qualified investigators and appropriate study centers; review of protocol procedures with the investigator and associated personnel before the study and periodic monitoring visits by the sponsor. Written instructions will be provided for administration and collection of study questionnaires.

Guidelines for CRF completion will be provided and reviewed with study personnel before the start of the study. The sponsor will review CRFs and patient questionnaires for accuracy and completeness after transmission to the sponsor; any discrepancies will be resolved with the investigator or designee, as appropriate. After upload of the data

into the clinical study database they will be verified for accuracy and consistency with the data sources.

### **3.4 Data Management and Storage Process**

#### **3.4.1 Data Management**

Data management and data quality check will be performed to remove errors and inconsistencies in order to assure the appropriateness of the study data set to assess the study objectives. Data entry screens will be developed and tested prior to initiating data collection to reduce data entry errors. If required, IMS will provide AbbVie with data for analysis.

Each site coordinator will be instructed to answer patients' queries which may arise in relation to the questionnaires and check the patients' input to make sure all questions are answered.

#### **3.4.2 Storage Process**

Following data quality checks, each dataset will be converted to SAS and merged for analysis. All information included in the CRF and the patients' questionnaires will be checked in order to detect possible queries to solve and will be extracted to a specifically designed database, where it will be validated by IMS personnel to ensure its quality. Finally, data analysis will be conducted and final results reported.

The databases will be stored in IMS data servers. Data servers are submitted to daily backups in order to increase the security on all data managed in the collection process.

All paper based questionnaires will be stored in a secured, locked area for a period of 7 years, after which all data will be shredded using an agency specialized in disposal of confidential documents.

### **3.5 Definitions of Study Variables**

The key variables of interest in this study are demographic and clinical characteristics, patient-reported health and disability outcomes, and healthcare resource utilizations. Most variables will be measured at baseline (i.e. index), and at weeks 12 and 24 after

the initiation of Adalimumab; healthcare resource utilization will be summarized over the 6 month post-index period.

### **3.5.1 Outcome/Endpoint Variables - Scoring of PRO Questionnaires**

#### **Health Assessment Questionnaire Disability Index (HAQ DI)**

In the HAQ DI, each category contains four response options ranging from 0-3, where 0 = without any difficulty and 3 = unable to do. In any event, a patient must have a score for at least six of the eight categories (i.e. Dressing and grooming, arising, eating, walking, hygiene, reach, grip, and activities). The HAQ DI's scoring conventions allow for the computation of two disability indices:

1. Standard HAQ DI (preferred and traditional scoring method; takes into account the use of aids/devices)

There are three steps:

- 1) Sum the 8 category scores by using the highest sub-category score from each category.
  - For example, there are three sub-category items in "Eating". A patient responds with a 1, 2, and 0, respectively; thus, the category score is 2.
- 2) Adjust for use of aids/devices and/or help from another person when indicated.
  - Adjust the score for a category by increasing a 0 or 1 to a 2.
  - If the patient's highest score is a 2, it would remain as 2.
- 3) Divide the summed category scores by the number of categories answered to obtain a HAQ DI score of 0-3 (3=worst functioning).

2. Alternative HAQ DI Score (without aids/devices)

There are two steps:

- 1) Sum the scores for each category, ignoring scoring for aids/devices
- 2) Divide by the number of categories answered (minimum 6 required). This yields a score of 0-3 (3=worst functioning).

#### **Short Form (36) Health Survey (SF-36)**

SF-36 scoring will be conducted by following these 7 steps in accordance to the developer's recommendations:

##### **Step 1: Data entry**

SF-36 scoring must ensure that the survey form is complete and the respondent's answers are unambiguous. If there are missing responses, using a scoring algorithm could derive scores across the eight SF-36 health domain scales for nearly all survey respondents. If there are multiple responses for a single item, the following rules are applied:

1. If a respondent marks two responses that are adjacent to each other, randomly pick one, and enter that number.
  2. If a respondent marks two responses that are not adjacent to each other, consider that item missing.
  3. If a respondent marks three or more responses, consider that item missing.
- Alternatively, one can opt to treat all items with more than one response as missing.

### **Step 2: Recoding item response values**

This is a process that derives the final item response values, or scores, to be used when calculating the raw scale scores for each health domain.

### **Step 3: Determining the health domain scale total raw scores**

Following item recording, which includes resolving items with missing data, a total raw score is computed for each health domain scale. The total raw score is the simple algebraic sum of the final response values for all the values for all the items in a given scale. The simple scoring method is possible because all the items in a given scale have roughly equivalent relationships to the underlying health construct being measured and because no item is used on more than one scale. As a result, it is not necessary to standardize or weight items.

### **Step 4: Transforming health domain scale total raw scores to 0-100 scores**

Health domain scale total raw scores are converted to 0-100 scores using the following formula:

$$\text{Transformed scale score} = \frac{(\text{Actual raw score} - \text{Lowest possible raw score})}{\text{Possible raw score range}} \times 100$$

### **Step 5: Transforming health domain scale 0-100 scores to T scores using health domain z scores**

The advantages of standardizing the health domain scales and converting 0-100 scores to norm-based scores using a T-score transformation are that health domain scale results can be meaningfully compared with each other and that these scores have a direct interpretation in relation to the distribution of scores in the 2009 US general population.

The first step is to convert the 0-100 scores into a linear z-score. A z-score would ensure each health domain scale has a mean of 0 and a standard deviation of 1 in the 2009 US general population. A z-score is computed by subtracting each health domain scale's 2009 US general population mean from the 0-100 score for that scale, and dividing the difference

by the given scale's standard deviation. Thus, the following formula is applied to convert 0-100 scores into z-scores:

$$Z\text{-score} = \frac{([0-100\text{ score}] - [83.29094])}{(23.75883)}$$

Z-scores are then transformed into T-scores (mean = 50, SD = 10) using the following formula:

$$T\text{-Score} = 50 + (z - \text{score} \times 10)$$

